#### 4.2.4. MRI Reporting and CAD/AI End Points

1. Sensitivity analysis of the CAD/AI system with histology and/or radiologist consensus as the reference standard
2. Comparison of radiologist diagnostic performance for detection of clinically significant cancer with and without the CAD/AI
3. The Interobserver agreement with and without the use of CAD/AI as second reader
4. Receiver operating characteristic (ROC) to compare the diagnostic performance of CAD/AI at different MAI scores.

#### 4.2.5. Other End Points

1. Changes in HRQOL measured by SF-12 at baseline and follow-up
2. Changes in worry and anxiety scores measured by CWS, PCQ and STAI
3. Rates of biopsy related adverse events (infectious complications, urinary retention, and haematuria requiring admission)
4. Linkage to national database\*
5. An open access secure and quality controlled databank of ultrasound and MRI meta-files matched with histopathology for future research and education.

\*The analyses of these end points will not be covered by the SAP.

[figure not shown]
## 5. General Considerations

### 5.1. Study Design

A prospective cross-sectional screening study with built-in feasibility assessment of a diagnostic cohort study.

The study design has been developed in accordance with STROBE (Strengthening the Reporting of Observational Studies in Epidemiology) guidelines (4) and the Consolidated Standards of Reporting Trials (CONSORT) statement (5).

5.1.1. Trial Schema

Imperial Clinical Trials Unit	STATISTICAL ANALYSIS PLAN	PROSTAGRAM
-------------------------------	---------------------------	------------

## 5.2. Study Population

Men aged between 50 and 69 years at average risk of prostate cancer based in the community will be invited to participate.

## 5.3. Eligibility Criteria

At the clinical screening appointment, the inclusion and exclusion criteria will be verified and eligible patients who wish to proceed will then provide informed written consent and will be enrolled in the study. Written informed consent will be obtained before any further procedures are undertaken and only once the potential participant is satisfied that all their questions have been addressed.

Individuals who are not eligible for the study will have the reasons for ineligibility recorded within a screening log.

### 5.3.1. Inclusion Criteria

1. Men aged between 50 and 69 years inclusive at the time of consent
2. Participants must be fit to undergo all procedures listed in the protocol
3. Estimated life expectancy of 10 years or more
4. An understanding of the English language sufficient to understand written and verbal information about the trial and consent process
5. Participants must be willing and able to provide written informed consent.

### 5.3.2. Exclusion Criteria

[figure not shown]
1. Previous PSA test or prostate MRI within the prior two years of screening/consent visit
2. Evidence of a urinary tract infection or history of acute prostatitis within the last 6 months
3. Previous history of prostate cancer, prostate biopsy or treatment for prostate cancer (interventions for benign prostatic hyperplasia/bladder outflow obstruction is acceptable)
4. Any potential contraindication to MRI, including but not limited to:
  - a. Devices or metallic foreign bodies such as pacemakers, implantable defibrillators, neurostimulators, cochlear implants, coronary stents, prosthetic heart valves, aneurysm clips and other intravascular devices
  - b. Previous history of hip replacement surgery, metallic hip replacement or extensive pelvic orthopaedic metal
  - c. Claustrophobia
5. Any potential contraindication to prostate biopsy
6. Dementia or altered mental status that would prohibit the understanding or rendering of informed consent.
7. Any other medical condition precluding procedures described in the protocol.

## 5.4. Withdrawal Criteria

Inability to conduct any of the imaging tests, blood tests or biopsies according to protocol.

## 5.5. Schedule of Time and Events

### 5.5.1. Patient Flow (CONSORT) Diagram

\*Providing participants meet the analysis population criteria outlined in Section 9.1 and Table 1 (Section 11.2.1).

### 5.5.2. Visit Schedule

	RECRUITMENT		Screening Visit	FOLLOW UP		
	Invitation	Telephone screening		Biopsy Visit	Final Visit (primary end point)	Long Term Follow up
Invitation, and flyer	x					
Screen for eligibility		x				
Explain screening procedures		x				
Informed consent			x			
Demographics, medical history, concomitant meds, clinical assessment			x			
Physical examination and DRE			x			
Questionnaires (SF-12, STAI, CWS, PCQ)			x	x	x	
PSA			x			
MRI			x			
Ultrasound			x			
Acceptability questionnaires (EBQ, PBQ)			x			
Episwitch and biobank samples (optional)			x			
Prostate Biopsy				x		
Adverse Event assessments and subject compliance			x	x	x	
Resource utilisation data					x	
Long term follow up data (optional)						x

This table includes the recommended schedule of events.

Imperial Clinical Trials Unit	STATISTICAL ANALYSIS PLAN	PROSTAGRAM
-------------------------------	---------------------------	------------

## 6. Sample Size Calculation

Screening tests are targeted at a large population of asymptomatic individuals, the majority of whom are healthy and do not have the target disease. The study is powered for the primary objective to determine the prevalence of screen-positive MRIs in the general male population aged 50-69 years. The low prevalence of positive findings from screening necessitate a large sample size to evaluate performance characteristics of screening tests.

The null hypothesis is that there is no difference in the proportion of men with a screen-positive MRI between the treatment groups.

We have followed the formula recommended by Naing et al (6) to determine an adequate sample size to estimate the prevalence of screen positive MRIs with a precision of +/- 5%:

$$n = \frac{Z^2 P(1 - P)}{d^2}$$

$Z$  = Z statistics for a level of confidence

$P$  = expected prevalence or proportion

$d$  = precision.

With reference to the calculations of the prevalence of screen-positive MRI (protocol v1.2), and using the formula by Naing et al. (6) above, assuming a prevalence of 19.6% requires a sample size of 243 participants. While assuming a prevalence of 61.1% will require a sample size of 366 participants. Allowing for a 10% dropout this requires a sample size of 270 and 406 participants respectively. The final, agreed, sample size was based on a prevalence of 61.1%, requiring 406 participants when allowing for a 10% dropout rate.

## 7. Randomisation and Blinding

### 7.1. Randomisation of Biopsy Lesion

If both the MRI and ultrasound are scored as suspicious by the relevant scoring system, these men will be randomised to have their ultrasound or MRI targeted biopsies first in order to reduce incorporation bias. This can occur as the biopsy tracts from the first lesion may influence the tracts of the second lesion.

A pseudo-randomisation was carried out by a random number generator in advance of the trial starting. Block randomisation was employed to keep the numbers in each group as similar as possible. A block size of 4 was chosen to reduce the chances that the biopsy order is inadvertently guessed by the operators. Allocation will be held by the Imperial Clinical Trials Unit and the order for lesions to be biopsied passed to the operating surgeon before the procedure begins.

### 7.2. Blinding of Screening Tests

In order to allow to limit reporter/reviewer bias all screening tests will be interpreted by an independent assessor blinded to the results of the other tests. In particular, the MRI and US report will be issued prospectively prior to any prostate biopsy. The pathologist will be blinded to the results of imaging/PSA.

It is not practical to fully blind the biopsy surgeon to the results of the screening tests, as the procedure will vary dependent on whether there is a lesion on the image-screening test. Therefore, the study team will inform the biopsy surgeon whether targeting needs to be incorporated into the biopsy strategy and the location of any areas suspicious on imaging.

This need for biopsy also means that it will not be feasible to fully blind participants to their screening result. However, if participants are informed of all their results this is a potential source of

Imperial Clinical Trials Unit	STATISTICAL ANALYSIS PLAN	PROSTAGRAM
-------------------------------	---------------------------	------------

attrition bias if participants selectively withdraw from undergoing biopsy based on the results of a single test. Participants may place undue emphasis on the image based screening tests at the expense of the PSA or biomarker test. To reduce the risk of selective withdrawal men who are recommended for biopsy will be informed that one or more of their screening test is positive. However, the specific test indicating a biopsy will not be made available to participants until after the prostate biopsy. Men who have a complete set of negative screening tests will be informed that no biopsy is required.

Men will be unblinded to the screening test results after having a biopsy or on exiting the trial due to negative screening tests. If a participant withdraws from the trial, they will be unblinded to their screening test result. There should be no other reasons for unblinding during the study.

### **7.3. Randomisation and Blinding of Double MRI Reporting**

To confirm the interobserver agreement of the MRI results assessed internally, 20% of the total MRI scans will be randomly selected to be double reported externally. The random selection will be stratified by PIRADS score: negative (a score of 1 or 2), intermediate (a score of 3), or positive (a score of 4 or 5). This double reporting will be undertaken by an independent radiology professor who will be blinded to the initial reading of the MRI scans.

## **8. Working Definitions**

### **8.1. Definitions of the Types of Cancer Detected**

#### **8.1.1. Definition of Clinically Significant Cancer**

There is no universally accepted histological definition of clinically significant prostate cancer. The definition has undergone significant changes over the years and it is expected that this dynamic process will continue. As there is no single agreed definition, clinically significant cancer will be defined across a range of thresholds.

At present, the definition which has general acceptance is (7):

- i. Gleason  $\geq 3 + 4$  (Grade Group (GrG)  $\geq 2$ ).

Other definitions include:

- ii. Any length of Gleason  $\geq 4 + 3$  (GrG  $\geq 3$ )
- iii. UCL/[name] definition 1: Gleason  $\geq 4 + 3$  and/or maximum cancer core length (MCCL)  $\geq 6\text{mm}$
- iv. UCL/[name] definition 2: Gleason  $\geq 3 + 4$  and/or maximum cancer core length (MCCL)  $\geq 4\text{mm}$
- v. Gleason  $\geq 3 + 4$  and/or maximum cancer core length (MCCL)  $\geq 6\text{mm}$ .

#### **8.1.2. Definition of Clinically Insignificant Cancer**

The following definitions correspond directly to those in Section 8.1.1.

The definition with general acceptance is:

- i. Gleason length of  $3 + 3$  (GrG 1).

Other definitions include:

- ii. Gleason length of  $3 + 3$ ,  $3 + 4$ , (GrG 1 + 2)
- iii. Those participants who do not meet the criteria in definition (iii) for clinically significant cancer
- iv. Those participants who do not meet the criteria in definition (iv) for clinically significant cancer

Imperial Clinical Trials Unit	STATISTICAL ANALYSIS PLAN	PROSTAGRAM
-------------------------------	---------------------------	------------

- v. Those participants who do not meet the criteria in definition (v) for clinically significant cancer.

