#### 8.1.3. Definition of No Cancer

The definition of no cancer is “there exists no presence of any cores that contain cancer”.

Analyses which are focused on the detection and diagnosis of clinically significant cancer, clinically insignificant cancer or no cancer will be repeated for all stated sets of definitions (i – v) above.

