#### 10.3.4. Clinically Significant/Insignificant and No Cancer

The thresholds for the type of cancer detected are calculated using the Gleason Score, maximum cancer core length (MCCL), and the definitions outlined in Section 8.1 separately.

Imperial Clinical Trials Unit	STATISTICAL ANALYSIS PLAN	PROSTAGRAM
-------------------------------	---------------------------	------------

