**Table 1: Primary Outcome Paper End Point Analysis**

	End Point	Analysis	Population
Primary End Point			
	Proportions of men with a screen-positive MRI defined by a score of 3 or greater (PIRADS and Likert)	Proportion with positive MRI score defined by a cut-off $\geq 3$ (PIRADS cut-off [1] and Likert cut-off [1] in Section 10.3.1)	Participants with MRI results 
Other Test Performance (MRI and US)			
	Proportions of men with a screen-positive MRI defined by a score of 4 or greater (PIRADS and Likert)	Proportion with positive MRI score defined by a cut-off $\geq 4$ (PIRADS cut-off [2] and Likert cut-off [2] in Section 10.3.1)	Participants with MRI results 
	Proportion of men with a screen-positive prostate ultrasound defined by a score of 3 or greater (US)	Proportion with positive ultrasound score defined by a cut-off $\geq 3$ (US cut-off [1] in Section 10.3.2)	Participants with ultrasound results 
	Proportion of men with a screen-positive prostate ultrasound defined by a score of 4 or greater (US)	Proportion with positive ultrasound score defined by a cut-off $\geq 4$ (US cut-off [2] in Section 10.3.2)	Participants with ultrasound results 
	Proportion of men with raised PSA level (defined as PSA $\geq 3.0\text{ng/mL}$ )	Proportion with raised PSA level (Section 10.3.3)	Participants with PSA results 
	Proportion of participants within each MRI score or US score of 1, 2, 3, 4 or 5	
 
Proportion within each value of Likert score
 
Proportion within each value of PIRADS score
 
Proportion within each value of US score
 
Histograms of distribution of each score (Likert, PIRADS and US) (Sections 10.3.1 & 10.3.2)
 
	Participants who completed the relevant test for the respective analyses 
	Proportion of participants across each MRI and US score with no cancer, insignificant cancer and significant cancer for each test	
 
Proportion within each value of Likert score detected to have each type of clinical cancer (Sections 8.1 & 10.3.1)
 
Proportion within each value of PIRADS detected to have each type of clinical cancer (Sections 8.1 & 10.3.1)
 
	Participants biopsied, and who completed the relevant test for the

Imperial Clinical Trials Unit	STATISTICAL ANALYSIS PLAN	PROSTAGRAM

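### SAP 8.1.2 definitions (iii) to (v) of insignificant cancer do not require cancer in any core, so a biopsied man with no cancer also counts as having insignificant cancer

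*SAP*

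**What the plan says.** SAP Section 8.1.1 lists five definitions of clinically significant cancer. Sets (i) and (ii) use Gleason grade alone; sets (iii) to (v) use Gleason grade and/or maximum cancer core length (MCCL).

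Section 8.1.2 gives the five matching definitions of insignificant cancer. Sets (i) and (ii) name grades: Grade Group 1, and Grade Groups 1 and 2. The other three are complements. Definition (iii) reads "Those participants who do not meet the criteria in definition (iii) for clinically significant cancer". Definitions (iv) and (v) use the same phrase and change only the number of the definition referred to.

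Section 8.1.3 defines no cancer once, for use with every set: "there exists no presence of any cores that contain cancer". It adds that analyses of the type of cancer "will be repeated for all stated sets of definitions (i – v) above". Section 10.3.4, which derives the analysis variable, relies on Gleason score, MCCL and "the definitions outlined in Section 8.1 separately". It adds no rule on exclusivity or precedence.

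Tables 1.2.6 to 1.2.9 print significant, insignificant and no cancer as three rows for each of sets (i) to (v). SAP Table 1 gives the population for the MRI and ultrasound versions as "Participants biopsied, and who completed the relevant test for the" respective analyses; the PSA version uses biopsied men with a PSA result. Both include men whose biopsy showed no cancer.

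**The concern.** A man with no cancer in any core has neither a Gleason grade nor a cancer core length. He cannot meet significant-cancer definition (iii), (iv) or (v), so he satisfies the matching insignificant-cancer definition as written. He also satisfies the no-cancer definition. The three rows printed for these sets are then not exclusive, and the insignificant row absorbs every benign biopsy.

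This matters because over-diagnosis of low-risk cancer is one of the harms the study is concerned with. Protocol Section 1.1 and SAP Section 2 list it among the risks of PSA screening, and SAP Section 2.1 presents its reduction as a possible advantage of MRI. The proportion of men with insignificant cancer at each test score is a secondary endpoint (SAP Section 4.2.1, items 6 and 7). In three of the five definition sets, the rule as written would give the wrong figure for it.

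**Working it through.** The plan states no figure on this point, so there is none to reproduce. The check is whether the written rules put each possible biopsy result in exactly one category.

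**Step 1: enumerate.** Take ten histology states: no cancer, and Gleason 3+3, 3+4 and 4+3, each with MCCL 2, 5 or 8 mm. Classify them by the text of Sections 8.1.1 to 8.1.3. The significant-cancer criteria are:

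- (iii) Gleason 4+3 or higher, and/or MCCL of 6 mm or more
- (iv) Gleason 3+4 or higher, and/or MCCL of 4 mm or more
- (v) Gleason 3+4 or higher, and/or MCCL of 6 mm or more

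| State | (iii) | (iv) | (v) |
|---|---|---|---|
| No cancer | **insignificant and none** | **insignificant and none** | **insignificant and none** |
| 3+3, 2 mm | insignificant | insignificant | insignificant |
| 3+3, 5 mm | insignificant | significant | insignificant |
| 3+3, 8 mm | significant | significant | significant |
| 3+4, 2 or 5 mm | insignificant | significant | significant |
| 3+4, 8 mm | significant | significant | significant |
| 4+3, any of the three lengths | significant | significant | significant |

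Under (i) and (ii) all ten states fall in exactly one category. Under (iii), (iv) and (v) the no-cancer state falls in two, and it is the only state that does.

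**Step 2: size.** In any table column, let N, I and S be the true proportions with no, insignificant and significant cancer, so N + I + S = 1.

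- Insignificant row as written: N + I = 1 − S
- Overstatement: (N + I) − I = N
- Sum of the three rows: S + (N + I) + N = 1 + N

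The first line also shows that the insignificant row would be the complement of the significant row and carry no separate information.

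**Step 3: illustrate.** The documents give no split, so these are assumptions.

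| No cancer / insignificant / significant | Insignificant, as written | Insignificant, exclusive | Sum of rows |
|---|---|---|---|
| 40 / 25 / 35% | 40 + 25 = 65% | 25% | 140% |
| 50 / 20 / 30% | 50 + 20 = 70% | 20% | 150% |
| 60 / 20 / 20% | 60 + 20 = 80% | 20% | 160% |

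Over a wider assumed range, with 30 to 70% no cancer and 10 to 20% significant, the row as written reads 80 to 90% (100 − 20 to 100 − 10). The exclusive figure runs from 10% (100 − 70 − 20) to 60% (100 − 30 − 10), and the rows sum to 130 to 170%.

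**Step 4: reach.** Which analyses use insignificant-cancer definitions (iii) to (v)?

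- Tables 1.2.6 to 1.2.9, insignificant rows, sets (iii) to (v), and the histograms of cancer type by score (Sections 11.2.3 and 11.7.1): affected.
- Primary endpoint: based on MRI score only; not affected.
- Sets (i) and (ii), and the significant-cancer and no-cancer rows of every set: not affected.
- Sensitivity, specificity, PPV and NPV: significant cancer against its absence (Section 11.2.3); not affected.
- False positives: based on no cancer, or on no cancer or Gleason 3+3 (Section 10.3.8); not affected.
- Hypothetical diagnostic pathways: limited to definition (i) by Sections 11.2.1 and 11.2.3 and a footnote to Table 1.2.14; not affected. Appendix 2, Table 2 lists all Section 8.1 definitions for that endpoint. If it were followed instead, the overlap could reach Table 1.2.14.

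**Step 5: test the remedy.** Limit (iii) to (v) to men with at least one core containing cancer. All ten states then fall in exactly one category under each set.

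**The case against.** The strongest reply is that the intent is plain. Section 8.1 is headed as defining types of cancer detected, the term being defined is itself a cancer, no cancer has its own definition, and the tables keep three rows apart. Gleason score and MCCL presuppose cancer in a core. On this view (iii) to (v) merely leave a word out, and a programmer who read them literally would see totals above 100% at the first table check.

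Most of that stands as a reading of intent: this is probably a drafting gap, and the wrong figures appear only if the text is programmed as written. It does not remove the point. The exclusion is stated nowhere, sets (i) and (ii) carry the condition that (iii) to (v) lack, and correcting it while programming would be an undocumented departure from a pre-specified rule.

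Two stronger readings are tempting, and neither is supported. A reader might infer that every screened man without significant cancer would be counted, since the definitions speak of participants. SAP Table 1 confines these analyses to biopsied men with the relevant test result. A reader might also infer that the study's whole assessment of over-detection fails. The primary objective is the MRI positive test rate, insignificant cancer is a secondary outcome, and the definition the SAP calls generally accepted, set (i), is sound. So is the pathway comparison built on it.

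**Conclusion.** The point holds on the wording. Definitions (iii) to (v) place biopsied men with no cancer in two categories, and no other part of the SAP resolves this. If programmed as written, the insignificant-cancer rows for three of the five sets in Tables 1.2.6 to 1.2.9, and the matching histograms, are too high by exactly the no-cancer proportion in the column. That identity needs no assumption about the data; the percentages shown above do, because the documents give no split. The affected output is secondary and descriptive. It should be corrected before analysis, but it does not threaten the primary result or the accuracy and pathway analyses as the methods text defines them.

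**What to change.** Reword Section 8.1.2 (iii) to (v) along these lines: *participants with at least one core containing cancer who do not meet significant-cancer definition (iii)/(iv)/(v)*. Add one sentence to Section 8.1 saying that, within each set, the three categories are mutually exclusive and sum to the table's own population, meaning biopsied men with the relevant test result. A sum to all biopsied men would be wrong where some lack that result. In the same edit, bring the Appendix 2 entry for the testing-combination endpoint into line with the limit to definition (i) in Sections 11.2.1 and 11.2.3.

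The cost is SAP wording only. No new data, added analysis or change in trial conduct is needed.

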#### 8.1.3. Definition of No Cancer

The definition of no cancer is “there exists no presence of any cores that contain cancer”.

Analyses which are focused on the detection and diagnosis of clinically significant cancer, clinically insignificant cancer or no cancer will be repeated for all stated sets of definitions (i – v) above.

### 8.2. Definition of a Positive Screening Test

Men will proceed to biopsy if any of the screening tests are positive. This includes:

[figure not shown]
- PSA: A raised PSA is defined as  $PSA \geq 3.0$ ng/ml as per UK screening guidelines.
- MRI: The presence of a discrete radiological score 3, 4 or 5 as scored by a radiologist or lesion on CAD/AI.
- Ultrasound: The presence of a discrete score of 3, 4 or 5 or prostate lesions on ultrasound.

Further threshold definitions for a screen-positive result for MRI and ultrasound will be analysed, as outlined in Sections 10.3.1 and 10.3.2.

